10.0 CRITERIA FOR REMOVAL FROM STUDY

Participants will be taken off study protocol under the following circumstances: 1) FDR voluntarily withdraws from study; 2) onset of severe cognitive impairment that makes participation in the study impossible, such as impaired ability to read or to provide accurate answers to the interviewer; 3) the participant expresses significant distress related to completion of the study assessments (the PI or a covering attending will refer the patient to clinical services if needed); or 4) if the study doctor believes it is in the participant's best interest to do so.

11.0 BIOSTATISTICS

Overview. This exploratory study is divided into two phases. Phase I involves in-home interviews of 25 participants to understand the factors that affect participants' decision-making about UVR protection (sunscreen use, shade-seeking, use of protective clothing). Qualitative data analyses will be carried out in Phase I to generate an Ethnographic Decision-Tree Modeling (EDTM) tree as described in Section 4.2. For example, a participant may be most likely to use sunscreen when it is a sunny day and when he/she is outdoors, at the beach, or at an outdoor sporting event. The participant may also state that he/she uses sunscreen whenever together with a young child, even though it may not be a sunny day.

In Phase II, we plan to recruit a sample of 60 melanoma first degree relatives (FDRs) and use IVR technology so that they can record their daily sun protection behaviors and decision criteria. The IVR system will call participants twice daily at approximately 12:30 pm and 5 pm for a period of 14 days. The participant will use their telephone keypad to answer a series of questions on their UVR protection behaviors, which will be four dichotomous, self-reported outcomes: sunscreen use, shade-seeking, hat use, and protective clothing use). The assessment will also address factors that affect UVR protection behaviors. These decision factors are based on the qualitative data we collected in Phase I. For example, we will ask participants to report the presence or absence of environmental factors (e.g., weather conditions), convenience/situational factors (e.g., availability of sun protection items), and social-interpersonal (e.g., activities engaged in). Data collected through IVR will generally be analyzed by Generalized Estimating Equations (GEEs) to explore the decision factors that promote or hinder the probability of UVR protection behavior.

Specific Aim I: To generate models explaining decision-making about three UVR protection behaviors (sunscreen use, shade-seeking, use of protective clothing) in melanoma FDRs.

Aim I will involve the EDTM methodology described in Section 4.2. Audio-recorded narrative data will be coded and summarized into an EDTM tree.

For example, decision factors such as convenience, weather, or social support for UVR protection may emerge as important factors. Because we are examining behaviors that involve highly complex interactions, we need to first understand the phenomenon more fully. Pertinent to Aim 1 is the use of descriptive statistics to summarize the sizes of the terminal decision nodes. Each node on the EDTM tree represents the pathway by which a person makes the decision to use or not to use UVR protection. The size of a terminal node in the EDTM tree represents the number of people who follow a specific decision

pathway. For example, we may find that many people do not use sunscreen if they do not find it before they leave home. In this hypothetical example, the decision factor of convenience trumps all other decision factors. We may therefore infer from the sizes of the nodes the importance of the corresponding decision pathways and specific decision splits. The most important advantage is that we will be better able to distinguish the factors that contribute to sunscreen nonuse from sunscreen use in order to separate the barriers from the facilitating decision factors.

Specific Aim II: To examine theory-driven affective and cognitive predictors of UVR protection maintenance (sunscreen use, shade-seeking, hat use, and use of UVR protective clothing) assessed in real time.

The general statistical paradigm for this Aim will be Generalized Estimating Equations (GEE) [83, 84] because of the repeated sampling of UVR protection behaviors and their predictors. Over a period of 14 days, each participant will generate a maximum of 28 assessments. Each assessment will yield 4 dichotomous outcome endpoints (sunscreen use, shade seeking, hat use and protective clothing). Additionally, each assessment will probe the decision factors, e.g., on environmental factors, convenience/situational factors, cognitive and social-interpersonal factors. For each outcome endpoint, we will fit a series of GEE models with a logit link. For example, we may fit the probability of sunscreen use as a function of weather (e.g., a dichotomous yes/no indicator of a sunny day). We will calculate the 95% confidence interval of the weather indicator on sunscreen use. The procedure will be repeated for other decision factors. We will use data visualization and graphs to summarize the 95% confidence intervals across decision factors, in the same exploratory procedures as outlined previously in O'Connor et al (2008).

Our exploratory GEEs approach is the most widely-used approach in the literature of intensive real-time data capture (aka Ecological Momentary Assessments, see Stone, 2009). Generally, these GEE models allow us to examine the extent to which each decision factor is associated with the health behaviors of interest. The repeated assessments will be clustered within persons. The working correlation structure will generally be fitted with an auto-regressive model because of the intensive daily assessments. The final number of covariates cannot be determined precisely at this time. However, care will be taken to minimize the number of confidence intervals to reduce concerns of multiple confidence intervals and to make the data more interpretable.

Power considerations.

We estimated the statistical power of a GEE model on sunscreen use. The GEE model has a single covariate (e.g., a weather indicator). An extensive literature search did not find prior data on UVR protection behaviors. However, we believe that an odds ratio of 1.55 is plausible and is not overly optimistic. A hypothetical example helps explain this 1.55 difference. Suppose on a given day, 30 people report that it is sunny and the other 30 report that it is not sunny. Then an odds ratio of 1.55 means that we will be able to detect a difference between 70% (21 / 30) and 60% (18 / 30) sunscreen use across the two groups. Our power calculation showed that a sample size of 60 would be adequate in detecting this 70% vs. 60% difference.

Our actual statistical power estimation was based on a more sophisticated Monte Carlo simulation approach [86] as we consider study attrition and missed assessments. Formulaic solutions for GEE power calculations were deemed inadequate for the current study because they do not apply (e.g., the present study involves no randomization to study arms [87, 88]). Our Monte Carlo simulation showed that, with a sample size of 60 melanoma FDRs, accounting for clustering effect, respondent attrition and missed assessments,

we will have 78% power to detect a 1.55 OR in a GEE predictor at a two-sided Type-I error rate of 0.01 (0.01 Type-I error to provide some control over multiple GEE models).

To account for correlated longitudinal sunscreen use data nested within study participants, we assumed in the power calculation an ARI correlation pattern with a 0.50 co-occurrence probability between two consecutive days of sunscreen use. This 0.50 co-occurrence probability was based on the expected co-occurrences if, at any given day, 21 of 30 respondents use sunscreen. We can use a simple 2x2 table to demonstrate that, with the fixed marginals at 21 on either day, the expected sunscreen use on both days is 15 persons (a joint probability of $0.50 = 15/30$, below).

		Day 2	
		Use sunscreen (n=21)	No use (n=9)
Day 1	Use sunscreen (n=21)	15 (21*21)/30	6
	No use (n=9)	6	3

This 0.50 co-occurrence rate between consecutive days of 0.70 sunscreen use translates into a tetrachoric correlation coefficient of 0.082 (by the commonprob2sigma() function in the R package bindata). We thus used a rounded 0.10 tetrachoric correlation between two consecutive days in our simulation of an ARI correlation matrix.

The simulations incorporated the following considerations of missing data. For rate of attrition, we assumed that 5% of the respondents will stop responding to the EMA assessments by the end of week 1, and 5% of the remaining respondents will be lost by the end of week 2. Thus, we assumed that we will retain 90% of the recruited respondents by the end of study period. Additionally, for any single assessment, there is a 30% probability that the assessment will be missing at random. We considered these missing data patterns because our prior LUCY data showed overall missing data patterns similar to these assumptions, so they are likely quite conservative given that LUCY subjects were quite ill.

Missing Data Analysis. Although we shall endeavor to obtain final evaluation data even for participants who discontinue the use of the hand-held device, we cannot rely on this and will use statistical methods appropriate when missing data may be informative. Data "missingness" may shed light on study features that affect feasibility. From our prior LUCY study we were able to attain a 89% completion rate for a 14-day period. This encouraging assessment completion rate notwithstanding, we will ascertain whether or not the number of completed IVR assessments differed between the sampling strata [78]. A significant difference will be evidence for missing not at random. For example, women may complete more assessments than men do over the 14-day assessment period. If missingness is not at random, we will consider imputing the missing data using several missing data imputation techniques [79-81]. These techniques are appropriate for different data types, including continuous, dichotomous, and count data. Additionally, one recently published data imputation technique by Demirtas and Bedeker is especially suitable for dichotomous and/or ordered longitudinal missing data [82]. We will also consider the use of Pattern-Mixture Model to control for non-ignorable missing patterns. Pattern-Mixture Model assumes that participants can be grouped into a small number of implicit cohorts with different patterns of missing data. One such implicit cohort may include participants who miss only a handful of assessments. Conceivably, there may be a cohort of participants who miss a few consecutive days of assessments. Pattern-Mixture Model can statistically adjust for participants' missing data pattern in order to account for missing not at

random. The method models the typical trajectories of responses within each of these cohorts and combines results across cohorts to make overall comparisons between groups of individual participants. Thus, Pattern-Mixture Model corrects the potential statistical bias due to missing not at random, and may help identify subgroups that show the lowest response rate to the EMA. There is a SAS macro for Pattern-Mixture modeling.

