1.0 PROTOCOL SUMMARY AND/OR SCHEMA

Understanding how people make decisions about ultraviolet radiation (UVR) protection is critical to the development of melanoma risk reduction interventions, since UVR exposure is the primary modifiable risk factor for melanoma. Strategies available for UVR protection include consistent sun avoidance and shade-seeking, as well as use of sunscreen, clothing, and hats. However, individuals at high risk for melanoma, including first-degree biological relatives (siblings, children, or parents) are inconsistent in their UVR protection behaviors [22-24]. This behavioral inconsistency is significant for health outcomes since even a few episodes of sunburn can greatly increase skin cancer risk. Understanding the decisions that govern variations in UVR protection would greatly improve our ability to influence these behaviors. While extensive prior research has examined the role of individual differences (such as intentions, beliefs, and demographic differences) in average levels of UVR protection, this study will focus on developing a measurement strategy to capture within-person variability, or level of consistency, in UVR protection.

To understand UVR protection decision-making, we will use a mixed qualitative and quantitative approach dictated by ethnographic decision tree modeling (EDTM; [1, 2]). This mixed model approach is a well-established approach to elucidating the process of decision-making by identifying factors that groups of people use to make real-life decisions that has been used in anthropology, sociology, and psychology for 25 years. The central goal of EDTM is to uncover and validate the criteria that influence decision making about a particular task. EDTM is distinct from other mixed model designs because EDTM addresses cognition around decision making in particular, making it highly relevant to our study goals.

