Using EDTM guidelines (described in greater detail on page 7), we will develop and establish the validity of decision models to explain daily decision-making about sunscreen use, shade-seeking, and UVR protective clothing use in melanoma first-degree relatives (FDRs). This study will involve two phases. In Phase I, we will conduct qualitative ethnographic interviews with 25 melanoma FDRs and generate a decision model for each UVR protection outcome for each melanoma FDR and then will construct a composite decision-making model incorporating findings across all 25 interviews for each of the three UVR protection outcomes (i.e., sunscreen use, shade-seeking, and UVR protective clothing use). Following this, in Phase II, we will establish the validity of the models using ecological momentary assessment of UVR protection (over 14 summer days, at 1 pm and 5 pm daily) in 60 different FDRs of 60 different melanoma patients. We will report on the level of success of the decision-making models in predicting behavioral performance. We will also examine the influence of between- and within-person changes in melanoma threat and efficacy, drawn from Witte's Extended Parallel Processing Model [3], as well as satisfaction with UVR protection maintenance, drawn from Rothman's theory of health behavior maintenance [4-6] on the three major outcomes of the study (i.e., sunscreen use, shade-seeking, and UVR protective clothing use). We will recruit equal numbers of women and men, and of those who perceive high and low advantages of tanning, to both phases of the study. The study will increase our understanding of the decision-making context of behavioral maintenance of UVR protection, and dictate strategies to reduce behavioral inconsistency - and increasing maintenance - of UVR protection in those at risk for melanoma and the general population.

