Health behavior theory may improve our understanding of the consistency of UVR protection. Witte's Extended Parallel Process Model [3] offers an account of the conditions under which illness threat may lead to health protective behavior. In the context of heightened illness threat (severity and susceptibility beliefs) and heightened beliefs that they can overcome the threat (self-efficacy and response-efficacy), people will act to do so via health protective behavior, or "danger control." In situations where threat is high but people don't believe they can manage it, behavioral avoidance, or "fear control" will result as people work to reduce their feelings of threat rather than their chances of becoming ill. Beliefs related to threat control include self-efficacy, or confidence that one can perform the behavior, and response-efficacy, or confidence that performing the behavior will protect against the health threat. Meta-analytic work examining this premise has found that pairing strong threat with high-self efficacy indeed maximizes behavior change [3]. In one of the only theories specifically addressing health behavior change maintenance, Rothman [50] has proposed and confirmed that satisfaction with the results of behavioral adoption - such as satisfaction with the results of smoking cessation or weight loss - determines whether individuals maintain health behavior over time [4, 5, 51].

We will examine these theory-based predictors - melanoma threat and efficacy, and satisfaction with UVR protection behavior - as between-subject and within-subject variables in this study. Accordingly, along with the most important decision factors, we will determine whether overall levels of these cognitive beliefs, or daily variations in these beliefs, are important in the maintenance of UVR protection over time in melanoma FDRs.

Study Significance. This is a measurement study aimed at understanding the discrete decision-making factors that dictate sun protection behavior on a daily basis. Given the clinical significance of even very few sunburn events, and the documented higher risk associated with some sun exposure contexts

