At each assessment session, they will be asked to respond to the question series using their telephone keypad. At approximately 12:30 pm they will be asked about their UVR protection and decision-making for the morning; and at approximately 5 pm, they will be prompted to complete this same assessment for the afternoon. At each time period after completing the IVR assessment, they will be prompted through the IVR system to record a brief (2-3 minute) description of their UVR protection strategies for that morning or afternoon. The IVR will allow a maximum of five minutes for the recording. The questions asking about sun protection use and decision making factors will follow a yes/no format to which they will respond using their telephone keypad. This format is a heavily-used, easy way to record health behaviors and decision-making factors consistent with EDTM. The IVR assessment survey will also include four closed-ended questions to assess: participants' perceived melanoma risk; perceived self-efficacy for following through with sun protection; beliefs about the effectiveness of sun protection in preventing melanoma; and level of satisfaction with decision to use/not use sun protection. Each assessment should require less than 10 minutes of the participants' time, keeping participant assessment burden low. Participants will have the option of being able to skip or refuse answering any questions they wish. Once the IVR has begun reading a question participants can interrupt the recording and move on by inputting their answer via the telephone keypad. The time at which participants complete the assessment will be electronically stamped on their assessment responses stored on the WEBCORE server. If the participant does not respond to the 1st call for each period (i.e., approximately 12:30 pm or approximately 5 pm), then the participant will automatically be called back up to 2 times within a one hour period. If the participant does not answer the 1st call for each period the system will leave the participant a voice mail message stating that they will be called back again shortly. If the participant does not answer the third follow-up call for a given time period the system will leave the participant a voice mail message stating that they will be called at the next assessment period. This same pattern will occur at the 5 pm assessment. Once the participant answers the call the IVR will not call again until the next assessment period. If the call is never answered, this assessment will not be able to be completed at a later time. However, the participant will be able to call the IVR system directly to complete the survey if they miss an outbound call for any assessment period.

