Demographic Questionnaire (Appendix R). We will ask a few demographic questions once the participant has consented as well as ask each person's experience with different kinds of electronic equipment. We expect the questionnaire to take less than 5 minutes to complete.

Interactive Voice Response (IVR) Diary Assessment - Phase II Only (Appendix C). The IVR diary assessment survey will be modeled on the composite decision model for each assessed sun protection behavior (sunscreen use, shade seeking, hat use, use of sun protective clothing) that was developed in Phase I. For each assessment (at approximately 12:30 and 5 pm daily), participants will receive an IVR call to report their sun protection attitudes and behaviors for that morning or afternoon. The IVR assessment survey asks participants to report on the following: 1) whether or not they have used each of the following sun protection methods: sunscreen, hats, shade-seeking, and protective clothing; 2) the presence or absence of 21 decision criteria identified in Phase 1 to influence sun protection decision making; and 3) theory-driven affective and cognitive predictors.

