In addition to answering questions about their sun exposure and protection through the IVR phone keypad, at the end of each assessment participants will be asked by the IVR to record an audio narrative diary that will capture their own thoughts about their sun protection choices during that assessed time period (i.e., either the morning or afternoon on a given day in the 14-day assessment period). The IVR will direct participants with the following instruction after participants complete the assessment at both approximately 12:30 pm and approximately 5 pm. "Please now speak into your phone to describe in your own words your use of sun protection during the time period(s) you have just reported on." After the instruction to record the audio narrative, the IVR will inform the participant the time at which they will receive their next call. Theory-driven affective and cognitive predictors will include perceived risk for melanoma and efficacy (UVR protection self- and response-efficacy) based on Witte's Extended Parallel Process Model [3]. We will assess these predictors at each assessment point, twice daily for 14 days. We have elected not to include melanoma severity in the assessment given that it is generally not found to be predictive of UVR protective behaviors in melanoma FDRs [22, 25]. To measure perceived risk for melanoma we will use one established question that has been used in prior UVR protection studies with melanoma FDRs [22-26]: B) perceived absolute likelihood with verbal anchors (1 = no chance, 2 = unlikely, 3 = moderate chance, 4 = likely, 5 = certain to happen),

Efficacy beliefs [72] will be assessed through two questions assessing the extent to which the participant feels capable of UVR protection in general (self-efficacy; 1="Not at all capable," 2="somewhat incapable," "3=somewhat capable," "4="extremely capable") and the extent to which the participant believes that UVR protection strategies can prevent melanoma (response-efficacy; 1="Not at all effective," 2= "a little effective," 3= "moderately effective," 4= "extremely effective").

We will also assess satisfaction with UVR protection consistent with Rothman's theory of health behavior maintenance [50] via one question adapted to satisfaction with UVR protection based on Rothman's work on satisfaction with smoking cessation [4, 5]. Accordingly, we will ask "How satisfied are you with your

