9.0 PRIMARY OUTCOMES

The following ultraviolet radiation protection (UVR) behaviors will be assessed as primary outcomes:

- Continuous sun avoidance and/or shade-seeking behavior
- Sunscreen use
- Use of UVR protective clothing
- Use of hats

Our first aim is to generate models explaining decision-making about three UVR protection behaviors (sunscreen use, shade-seeking, use of protective clothing) in melanoma FDRs. We will model daily decision-making processes for UVR protection through qualitative and quantitative research strategies. In Phase I, we will conduct in-home ethnographic interviews with 25 melanoma FDRs and generate a decision making model for each UVR protection behavior for each melanoma FDR, and subsequently construct a composite decision-making model for each of the UVR protection outcomes (i.e., sunscreen use, shade-seeking, and UVR protective clothing use) representing prominent decision making factors across all 25 FDRs interviewed. In Phase II we will establish the validity of the models via examination of daily decision-making about UVR protection using ecological momentary assessment via IVR (over 14 days in the summer/early fall, at approximately 12:30 pm and 5 pm daily) in 60 different melanoma FDRs from Phase I. As outlined in EDTM methodology, we will report on the level of success of the decision-making model in predicting uptake of each of the three UVR protection strategies.

Our second aim is to examine theory-driven affective and cognitive predictors of UVR protection maintenance (sunscreen use, shade-seeking, hat use, and use of UVR protective clothing) assessed in real time. We will examine the role of melanoma threat and efficacy beliefs in determining UVR protection maintenance drawn from Witte's Extended Parallel Processing Model [3], and will examine the role of satisfaction in UVR protection maintenance drawn from Rothman's theory of health behavior maintenance

[4-6]. We will examine both between-person and within-person changes in these predictors, as well as salient decision-making factors (Identified in Aim I), in predicting maintenance of sunscreen use, shade-seeking, hat use, and use of UVR protective clothing.

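### Aim II promises between-person and within-person effects of the theory predictors, but the analysis as stated yields one coefficient per predictor that mixes the two

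*Combined protocol and SAP*

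**What the plan says.** **The promise.** Section 1.0 states "We will also examine the influence of between- and within-person changes in melanoma threat and efficacy", and the same sentence goes on to satisfaction. Section 3.0 treats these theory predictors as variables of both kinds, between and within subjects, and puts the question as: "we will determine whether overall levels of these cognitive beliefs, or daily variations in these beliefs, are important in the maintenance of UVR protection". Section 9.0 repeats it: "We will examine both between-person and within-person changes in these predictors, as well as salient decision-making factors".

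**The measurement.** Section 4.2 says "The IVR assessment survey will also include four closed-ended questions to assess" perceived melanoma risk, self-efficacy, response-efficacy and satisfaction. Section 7.0 says of the risk and efficacy items: "We will assess these predictors at each assessment point, twice daily for 14 days". The satisfaction item asks about the morning or afternoon just reported. All four can therefore differ between people and from one assessment to the next.

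**The analysis.** Section 11.0, Specific Aim II, says: "For each outcome endpoint, we will fit a series of GEE models with a logit link". The example regresses sunscreen use on a yes/no weather indicator, and the same step is then taken for other factors. Assessments are clustered within persons, generally with an autoregressive working correlation. Section 11.0 gives no person-mean term, centring, aggregate covariate or other route to two coefficients per predictor.

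**The power.** Section 11.0, Power considerations, gives 78% for an odds ratio of 1.55 at two-sided 0.01 with 60 people, in a GEE with a single covariate. It does not say whether that covariate varies over time within a person.

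**The concern.** Section 3.0 asks whether a person's usual level of belief matters, or the day's departure from it. These are different effects and can differ in size. A raw predictor that varies both ways has one coefficient, which is a weighted mixture of the two. Clustering by person and an autoregressive working correlation deal with dependence in the outcome; they do not split the predictor. If the analysis follows the illustration, an odds ratio above 1 for self-efficacy could mean that confident people protect themselves more, that people protect themselves more on confident days, or both. The level-versus-variation question would then stay open although the data to answer it are collected.

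**Working it through.** **1. The plan's own figure.** Inputs from Section 11.0: 60 people; up to 28 assessments; 70% versus 60% use, so OR = (0.70/0.30)/(0.60/0.40) = 1.556; AR(1) tetrachoric correlation 0.10; 30% of assessments missed; 5% then 5% attrition (0.95 × 0.95 = 90.25% retained); two-sided alpha 0.01. A simulation with a logit GEE, AR(1) working correlation and robust standard errors (4,000 runs) gives 77.9% when the covariate is fixed per person (30 versus 30) and 82.6% when it varies freely within person. A two-proportion check under independence gives 80% to 84%. The stated 78% reproduces.

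**2. What the single coefficient estimates.** Let m_i be person i's expected predictor value, W and B the within- and between-person odds ratios, and s the between-person share of predictor variance:

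logit P(Y) = logit(0.65) + ln W·(x − m_i) + ln B·(m_i − mean).

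Under working independence the single coefficient is close to s·ln B + (1 − s)·ln W. With ln 1.55 = 0.438 and s = 0.50, either case gives exp(0.219) = 1.24. The documents give neither s nor the effect sizes, so both are assumed.

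| Share s | 5% | 15% | 30% | 50% |
|---|---|---|---|---|
| Only between real, formula | 1.02 | 1.07 | 1.14 | 1.24 |
| Only between real, simulated AR GEE | 1.02 | 1.06 | 1.14 | 1.22 |
| Only within real, formula | 1.52 | 1.45 | 1.36 | 1.24 |
| Only within real, simulated AR GEE | 1.50 | 1.46 | 1.37 | 1.27 |

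These are for a binary predictor. A 1-to-4 rating gives nearly the same per point (1.02/1.06/1.12/1.22 and 1.52/1.46/1.37/1.27). Simulation under working independence gives 1.02/1.06/1.15/1.24 and 1.50/1.45/1.36/1.26, so the AR structure is not the cause. With both effects at 1.55 the single odds ratio is about 1.55, and there is no harm.

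**3. What a split recovers.** With person mean and deviation both in the model, the within-person odds ratio comes back as 1.00 or 1.55 to within about 0.03. The between-person term is less clean, because the person mean is estimated from about 28 × 0.70 × 0.95 ≈ 19 assessments. Its reliability is roughly s/(s + (1 − s)/19). At s = 5% that is 0.05/(0.05 + 0.05) = 0.50, so with W = 1 a true 1.55 appears as exp(0.50 × 0.438) = 1.24. Simulation gives 1.24/1.39/1.47/1.51 at 5/15/30/50%.

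**4. Power after the split.** Plan's inputs, both odds ratios 1.55, alpha 0.01, 2,000 runs:

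| Share s | 5% | 15% | 30% | 50% |
|---|---|---|---|---|
| Within-person | 78% | 74% | 62% | 44% |
| Between-person | 10% | 18% | 30% | 47% |
| Within-person, 0.10 as a stable person effect | 80% | 76% | 64% | 46% |
| Between-person, 0.10 as a stable person effect | 6% | 9% | 14% | 23% |

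The last two rows treat the plan's 0.10 outcome correlation as a lasting difference between people instead of a serial one. Under that change the one-coefficient power for a covariate fixed per person drops from 78% to 46%. With an assumed person-level outcome correlation of 0.3, between-person power is only 4% to 11% (predictor clustering 0.2 to 0.8). Low between-person power at small shares is partly built in, since little between-person variance is left to detect.

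**The case against.** The study calls itself exploratory, presents the weather model only as an example, leaves the number of covariates open, and refers to a published analysis that cannot be consulted here. Section 3.0 already comes close to an operational definition by distinguishing overall levels from daily variation. A capable analyst could read that and split the predictors unprompted. This stands: nothing in Section 11.0 forbids a split, so the gap is one of specification. It does not close the gap, because the stated intention to keep confidence intervals few works against adding a second term that was never planned.

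Three stronger readings are tempting, and the documents do not support them.

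- A reader might infer that the 78% is wrong or claims too much. It reproduces, and it is presented openly as the power for one covariate; it never claims to cover two effects per belief.
- A reader might infer from Section 1.0, "this study will focus on developing a measurement strategy to capture within-person variability, or level of consistency, in UVR protection", that splitting predictors is the study's main purpose. That sentence concerns variability in the outcome behaviour.
- A reader might infer that the decision factors are promised both ways too. The Section 9.0 sentence can equally list them as a separate item, and Section 3.0 asks the level-or-variation question only of the beliefs.

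**Conclusion.** The point holds for the four theory predictors. The plan promises two effects per predictor and states a model that, used as illustrated, gives one. When the effects differ, the single odds ratio equals neither: about 1.02 to 1.24 if only a between-person 1.55 is real, and about 1.51 down to 1.24 if only a within-person 1.55 is real, for assumed shares of 5% to 50%. At a 50% share the two opposite answers look almost the same. At small shares the single coefficient is close to the within-person effect and the distortion is slight; with equal effects there is none. The missing specification itself depends on no assumed share.

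The 78% stands for what it describes but does not carry over to each split effect. The power ranges above rest on assumed shares and equal effects of 1.55, and the between-person figures are especially sensitive to how far people differ stably in sun protection. This is an improvement worth making, not a contradiction or an arithmetic error.

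**What to change.** In Section 11.0, Specific Aim II, state that perceived risk, self-efficacy, response-efficacy and satisfaction each enter the GEE as two terms: the person's mean over completed assessments, and the deviation from that mean. Report both odds ratios with robust 95% confidence intervals, and each predictor's between-person share of variance. Ask the sponsor whether Section 9.0 intends the same for decision factors, and split those only if so.

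In the power section, state that 78% is for one coefficient in a one-covariate model and whether that covariate varied over time. Re-run the simulation for each effect over a stated range of shares, with and without stable person differences in the outcome.

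The cost is SAP wording and a re-run simulation, with no new data. The downsides should be stated:

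- There are 4 predictors × 4 outcomes = 16 more intervals, against the aim of keeping them few. Each decision factor split would add 4 more. Section 7.0 lists "the presence or absence of 21 decision criteria identified in Phase 1 to influence sun protection decision making", so splitting all of them would add 21 × 4 = 84.
- The person-mean odds ratio is pulled toward the within-person one when the share is small (about 1.23 to 1.24 for a true 1.55 at a 5% share).
- Satisfaction is asked after the behaviour, about that period's decision (Section 7.0). Its within-person coefficient should be reported as an association, not as a daily effect on the decision.
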